**After the preceding procedures and assessments are completed:**

- Study drug administration (record date and time of dose of study drug)
- Vital sign measurements (sitting blood pressure, heart rate, respiratory rate, oral temperature) and pulse oximetry will be performed at 15, 30, and 45 minutes after the start of the infusion and at completion of the infusion

**After administration of study drug, the following post treatment procedures and assessments will be performed:**

- Vital sign measurements (sitting blood pressure, heart rate, respiratory rate, oral temperature) and pulse oximetry: 30 minutes, 1 hour, and 2 hours following completion of the infusion; abnormal results to be repeated after 5 minutes of rest
- PK sample collection at 5 minutes and 1 and 2 hours after the completion of study drug infusion; record collection date and time for each PK sample
- 12-lead ECG (to be obtained in triplicate approximately 5 minutes after the completion of study drug infusion)

**Throughout the study visit, the following assessments will be performed:**

- Concomitant medication assessment
- AE assessment

### **8.3.3 Cohort 2: Follow-up Day 112**

For Cohort 2 Day 112 ( $\pm$  5 days), subjects are to return to the clinic and the following procedures are to be performed:

- Vital sign measurements (after 5 minutes of rest; sitting blood pressure, heart rate, respiratory rate, oral temperature): abnormal results to be repeated after 5 minutes of rest
- Clinical safety laboratory tests (hematology, serum chemistry panel, urinalysis)
- PDAI
- Immunogenicity sample collection
- PD sample collection
  - IgG, IgG subtypes (IgG1-4), IgA, IgM
  - CIC
  - Anti-Dsg (1 and 3) antibody titers
  - C3
  - AECA
  - Exploratory pemphigus immune response biomarkers
- Photography
- Concomitant medication assessment
- AE assessment

#### **8.4 All Cohorts: End of Study or Early Termination Visit; Cohort 1, Day 112; Cohort 2, Days 91 and 140**

For Cohort 1 Day 112 ( $\pm 5$  days) and Cohort 2 Days 91 and 140 ( $\pm 5$  days), subjects are to return to the clinic and the following procedures are to be performed:

- Complete physical exam
- Vital sign measurements (after 5 minutes of rest; sitting blood pressure, heart rate, respiratory rate, oral temperature): abnormal results to be repeated after 5 minutes of rest
- Clinical safety laboratory tests (hematology, serum chemistry panel, urinalysis)
- Pregnancy test
- 12-lead ECG (to be obtained in triplicate after 5 minutes of rest in the supine position) (*Cohort 2, Days 91 and 140 only*)
- Serum tetanus antibody and VZV antibody
- PDAI
- Immunogenicity sample collection
- PD sample collection
  - IgG, IgG subtypes (IgG1-4), IgA, IgM
  - CIC
  - Anti-Dsg (1 and 3) antibody titers
  - C3
  - AECA
  - RNAseq (*Cohort 1 Day 112; Cohort 2, Day 91 only*)
  - Urine IgG (*Cohort 1 only*)
  - Immunophenotyping (*Cohort 2, Day 91 only*)
  - Exploratory pemphigus immune response biomarkers
- Photography
- HR-QoL (ABQoL, Skindex-29) (*Cohort 2 only*)
- Concomitant medication assessment
- AE assessment

**Note:** a subject may choose to terminate participation in the study at any time. Under this circumstance, the subject will be encouraged to return as soon as possible for an early termination visit and to receive assessments otherwise scheduled on Day 112 (Cohort 1) or Day 91 (Cohort 2).

## **9. STUDY RULES**

### **9.1 Subject Withdrawal**

Every reasonable effort will be made to keep the subject in the study; however, if a subject withdraws from the study, the Investigator should complete and report the reasons for withdrawal as thoroughly as possible. The reason(s) for termination must be clearly documented on the appropriate page of the eCRF.

Subjects who have received at least one SYNT001 dose and withdraw or prematurely discontinue study drug should be encouraged to attend, at a minimum, the early termination (ET) visit Day 112 (Cohort 1) or Day 91 (Cohort 2). Subjects in Cohort 2 will also be encouraged to attend the remaining follow up visits on Days 112 and 140.

If the subject fails to return for these assessments for unknown reasons, every effort (eg, telephone, email, and letter) should be made to contact them.

The reason(s) for a subject's participation in the study may be prematurely discontinued will be documented and include:

1. The subject wishes to withdraw from the study.
2. Request by a regulatory agency or Institutional Review Board).
3. The subject experiences a significant or intolerable AE.
4. The subject experiences a significant adverse change in vital signs, physical examination findings, or clinical laboratory parameter.
5. The subject has a need for a concomitant medication that is not permitted by the study protocol.
6. The subject experiences generalized impairment or mental incompetence that would result in the subject being unable to understand his or her participation in the study.
7. If, in the Investigator's medical judgment, further participation would be injurious to the health and well-being of the subject, or is not in the best interest of the subject.
8. Administrative reasons, such as subject non-compliance or a major protocol violation.

If at the discretion of the Investigator with consultation with the Medical Monitor, a subject requires a significant increase in dose(s) of anti-pemphigus medication(s) for the management of pemphigus, the subject should be encouraged to attend, at a minimum, the ET visit Day 112 (Cohort 1) or Day 91 (Cohort 2). Subjects in Cohort 2 will also be encouraged to attend the remaining follow up visits on Days 112 and 140.

### **9.2 Subject Replacement**

Enrolled subjects withdrawn for a reason other than an AE may be replaced.

### 9.3 Study Discontinuation

The Sponsor has the right to terminate or to stop the study at any time. Reasons for study discontinuation may include, but are not limited to, the following:

- The incidence or severity of AEs in this or other related studies indicates a potential health hazard to subjects
- Subject enrollment is unsatisfactory
- Drug supply issues
- Excessive subject self-withdrawal
- Significant protocol violations (eg, violation of eligibility criteria, dosing errors, missing data for study endpoint analysis)

### 9.4 Lost to Follow-up

All reasonable efforts should be made to contact any subject lost to follow-up during the study to complete assessments and retrieve any outstanding data. If the subject is unreachable after three good faith attempts, **at a minimum, the Investigator should follow up with a registered letter requesting contact** so safety data may be collected, recorded, and reported (if necessary).

### 9.5 Stopping Rules

#### 9.5.1 Dose-Escalation Stopping Rule (Cohort 1)

Dose recommendations will be made by a DEC and will be based on safety and PD evaluations including but not limited to, DLTs, AEs, SAEs, and total IgG levels.

Dose-limiting toxicity (DLT) will be defined generally as severe (Grade 3) AEs occurring in  $\geq 2$  subjects that are determined to be clinically significant and considered related to study drug.

If 2 or more subjects at any time in any cohort have Grade 3 AEs that are determined to be clinically significant and considered to be related to study drug, dosing will be halted within that cohort and dose-escalation to a higher dose will not occur. Upon review of the available information, the DEC may reduce the dose by at least 50% prior to enrolling additional subjects.

#### 9.5.2 Study Stopping Rule

If any subject at any time experiences a life-threatening AE (Grade 4) that is considered to be related to study drug, any further dosing in all enrolled subjects will be suspended until the Sponsor Medical Lead has evaluated the event and determined the next appropriate course of action. At any time during the study, the study may be discontinued if the Sponsor Medical Lead determines that further drug exposure would pose an undue risk to subjects.

#### 9.5.3 Individual Stopping Rule

Dosing for any individual subject will be discontinued (ie, no further study drug will be given to that subject) if the subject experiences any study drug-related SAE or any study drug-related

non-serious AE that, in the judgement of the Investigator (following consultation with the Medical Monitor, if desired) or in the judgement of the Sponsor Medical Lead, suggest that it could be unsafe to administer further study drug to that subject.

Subjects who withdraw from this study due to an AE determined to be related to study drug are to be followed until there is:

- Resolution or stabilization of the AE determined to be related
- The subject is lost to follow-up
- The event is otherwise explained

If there is a persistent AE contributing to discontinuation that is determined to be related to SYNT001, subjects must be followed with appropriate medical management until resolution or stabilization. Refer to [Section 10](#) for more information.

Additionally, a subject will be discontinued from further treatment with study drug, at the discretion of the Investigator with consultation with the Medical Monitor, if they require a significant increase in doses of anti-pemphigus medications for the management of pemphigus.

## 10. EVALUATION OF SAFETY

### 10.1 Safety Parameters

Subjects will be monitored continuously throughout the treatment and follow-up period for AEs (acute, delayed, and/or cumulative), as well as for changes in clinical status. Parameters measure/assess safety include physical examinations, vital sign measurements (including pulse oximetry), clinical (safety) laboratory tests (hematology, serum chemistries, urinalysis), concomitant medication assessments, and ECG. Clinical and laboratory AEs will be graded using the NCI CTCAE; Version 4.03 (see [Appendix 1](#)).

### 10.2 Adverse Events

An AE is defined as any untoward medical occurrence in a clinical trial subject associated with the use of a drug, whether considered drug related or not. An AE can be an unfavorable and unintended sign (eg, an abnormal laboratory value finding), a symptom, or a disease temporally associated with the use of a drug, without judgment as to causality. An AE can arise from use of the drug (eg, use in combination with another drug) and from any route of administration, formulation or dose, including an overdose. An AE also includes, but is not limited to, any clinically significant worsening of a pre-existing condition. Examples include:

- Any sign, symptom, physical finding, or laboratory result that has worsened in nature, severity or frequency compared to baseline
- Reactions from an investigational drug, including those occurring because of an overdose, abuse of the study drug, withdrawal phenomena, sensitivity or toxicity
- Concurrent illness that was not present or worsens in nature, severity, or frequency compared to baseline
- Injury or accident
- Exacerbation of a pre-existing condition

Pregnancy is not considered an AE or SAE; however, any pregnancy complication(s) should be recorded as an AE(s) or SAE(s) (if applicable). Elective abortions without complications should not be regarded as AEs, unless they were therapeutic abortions. Hospitalization for normal delivery of a healthy newborn should not be considered an SAE. If a female subject becomes pregnant during the conduct of the study, the Investigator must notify the Sponsor according to the procedures provided in [Section 10.5.4](#).

Planned hospitalization admissions or surgical procedures for a condition known to exist before the subject signed the informed consent are not an AE and should be recorded as medical history. If the planned hospitalization or procedure is executed as planned and without complication, the record in the subject's medical history is considered complete. However, if the event/condition deteriorates in an unexpected manner during the study or following surgery, it must be reported as an AE according to the procedures provided in [Section 10.2.1](#).

### 10.2.1 Recording an Adverse Event

For data collection, all untoward events that occur after informed consent through the last study visit are to be recorded on eCRFs by the investigational site. All AEs are to be accurately recorded on the **Adverse Event** page of the subject's eCRF. The severity of each AE will be graded using the NCI CTCAE, Version 4.03 (see [Appendix 1](#)). The date of onset as well as the end date of the event should be recorded or the event should be entered as "ongoing". In addition, the method used to treat the AE and the outcome of the AE will be noted. The Investigator will assess the relationship of the event to study drug.

### 10.2.2 Assessment of Causality

A medically qualified Investigator must assess the relationship of any AE (including SAEs) to the use of the study drug, as related or not related, based on clinical judgment and using all available information. The causal relationship between the study medication and the AE will be assessed using one of the following categories:

**Not Related:** Factors consistent with an assessment of Not Related include:

- Temporal relationship is lacking (eg, the event did not occur within a reasonable time frame following administration of the study medication); or
- Other causative factors more likely explain the event (eg, a pre-existing condition, other concomitant treatments).

**Related:** Factors consistent with an assessment of Related include:

- There is a positive temporal relationship (eg, the event occurred within a reasonable time frame following administration of study medication); or
- The AE is more likely explained by the investigational product than by another cause (ie, the AE shows a pattern consistent with previous knowledge of the investigational product or the class of the investigational product)

### 10.2.3 Serious Adverse Events

*(Notify Medpace Safety within 24 hours; document on eCRF)*

The SAE definition and reporting requirements are in accordance with Title 21 Part Code of Federal Regulations (CFR) 312.32 and the Guidance for Industry and Investigators Safety Reporting Requirements for Investigational New Drug (INDs) and Bioavailability /Bioequivalence Studies.

An AE is considered "serious" if, in the view of either the Investigator or sponsor, it results in any of the following outcomes:

- **Death:** This includes any death that occurs while the subject is "on study" through the last study visit.

**Note:** Death is an outcome of an AE and not an AE. The event(s) that caused death (eg, illness, accident) is the SAE. Death due to any other cause(s) must also be reported as an outcome of the reportable SAE.

- **Life-threatening adverse drug event:** An AE or suspected adverse reaction is considered “life threatening” if, in the view of either the Investigator or Sponsor, its occurrence places the patient or subject at immediate risk of death. It does not include an AE or suspected adverse reaction that, had it occurred in a more severe form, might have caused death.
- **Inpatient hospitalization or prolongation of existing hospitalization:** an AE that requires admission to a hospital for medical and/or surgical intervention.
- In the absence of an AE, the Investigator should not report hospitalization or prolongation of hospitalization as an SAE, as detailed in the following examples:
  - An elective or previously scheduled surgery for a pre-existing condition that has not deteriorated unexpectedly after initiation of treatment (eg, a previously scheduled ventral hernia repair)
  - Hospitalization or prolongation of hospitalization is needed for a procedure required by the protocol
  - Hospitalization or prolongation of hospitalization is part of routine procedure followed by study center
  - Hospitalization for survey visits, annual physicals, or planned observation
  - Hospitalization for observation with release within 24 hours (eg, an emergency room visit for hematuria that results in a diagnosis of cystitis and discharge to home on oral antibiotics)
- **Persistent or significant incapacity or substantial disruption of the ability to conduct normal life functions**
- **Congenital anomaly/birth defect**
- **Important medical event:** An event that may not result in death, be life threatening, or require hospitalization may be considered an SAE when, based upon appropriate medical judgment, it may jeopardize the subject and may require medical or surgical intervention to prevent one of the outcomes listed in this definition.

### 10.2.3.1 Recording a Serious Adverse Event

When the diagnosis of an SAE is known or suspected, the Investigator should record the diagnosis or syndrome as the primary SAE term, rather than as signs or symptoms. Signs and symptoms may then be described in the event description. For example, dyspnea should not be used as an SAE term if the diagnosis, which caused the dyspnea, is known to be malignant pleural effusion.

Death should not be recorded as an SAE, but as an outcome of a specific SAE, unless the event preceding the death is unknown. In the exceptional case where the events leading to death are unknown, then death may be used as an event term. If an autopsy was performed, the autopsy the autopsy report should be provided.

### 10.2.3.2 Reporting a Serious Adverse Event

#### RESPONSIBILITIES OF THE INVESTIGATOR

Any death, SAE, or pregnancy, experienced by the subject after informed consent through the last study visit, regardless of relationship to study drug, must be promptly reported (within 24 hours of the Investigator becoming aware of the event) by telephone or electronic transmission to the Sponsor (or designee).

Contact information for SAE reporting:

Medpace Clinical Safety  
Medpace SAE hotline:  
Telephone: PPD [redacted] dial P or PPD [redacted] dial P  
Facsimile: PPD [redacted] or PPD [redacted]  
e-mail: PPD [redacted]

Additionally, the Investigator will be able to contact the **Medical Monitor**:

#### Medical Safety Contact

PPD [redacted]  
Phone (EU): PPD [redacted] extension PPD [redacted]  
Mobile phone: PPD [redacted]  
Email: PPD [redacted]

The Investigator will report the SAE to his or her IRB in accordance with IRB's standard operating procedures and policies. Adequate documentation must be maintained showing that the IRB was properly notified.

SAEs must be recorded on the SAE form in the electronic data capture (EDC) system. This requirement includes all SAEs that occur after informed consent through the last study visit. The minimum information required for SAE reporting includes identity of investigator, site number, subject number, an event description, SAE term(s), onset date, the reason why the event is serious (ie, the seriousness criteria), and the Investigator's assessment of the relationship of the event to study treatment. Additional SAE information including medications or other therapeutic measures used to treat the event, action taken with the study treatment due to the event, and the outcome/resolution of the event will be recorded. Paper forms for reporting SAEs will be provided to the study sites as back-up in case the EDC system is not accessible.

In all cases, the Investigator should continue to monitor the clinical situation and report all material facts relating to the progression or outcome of the SAE. Furthermore, the Investigator may be required to provide supplementary information as requested by the Sponsor (or designee).

## **RESPONSIBILITIES OF THE SPONSOR (OR DESIGNEE)**

The Sponsor (or designee) will process and evaluate all SAE as soon as the reports are received. For each SAE received, the Sponsor will decide as to whether the criteria for expedited reporting have been met.

The Sponsor (or designee) is responsible for promptly informing the FDA and other regulatory authorities as well as other participating Investigators of the event. Written submission must be made by the Sponsor to the FDA as soon as possible and in no event later than 15 calendar days after the Sponsor's initial notification of the event, or for an event that is fatal or life-threatening no later than 7 calendar days after the Sponsor's initial notification.

### **EXPEDITED REPORTING**

Under FDA ruling (US Code of Federal Regulations, Title 21 CFR Part 312.32) and the ICH Guideline "Clinical Safety Data Management: Definitions and Standards for Expedited Reporting E2A," the Sponsor is required to submit written documentation, in the form of a safety report, detailing:

- Any event associated with the use of the drug, that is both serious and unexpected, or
- Any finding from tests in laboratory animals that suggests a significant risk for human subjects, including reports of mutagenicity, teratogenicity, or carcinogenicity.

The Sponsor will submit SAEs that meet the criteria for expedited reporting to the regulatory authorities in accordance with local regulations governing safety reporting.

#### **10.2.4 Follow-Up of Adverse Events and Serious Adverse Events**

Any SAE or AE must be followed until either resolution of the event or determination by the Investigator that the event has become stable or irreversible. Appropriate diagnostic tests should be performed and therapeutic measures, if indicated, should be instituted until the event has returned to baseline or until a clinically satisfactory resolution has been achieved. The appropriate follow-up visits must be scheduled and the specific tests repeated or performed as necessary. The status of all AEs will be documented as of the last study visit. If all required information is not available at the time of the initial report, follow-up information will be completed in the EDC system.

### **10.3 Warnings and Precautions**

#### **10.3.1 Vaccinations**

Subjects must not receive any vaccinations from within 2 weeks of screening until 28 days following final dose of study drug.

#### **10.3.2 Management of Allergic or Infusion-Related Reactions**

As observed with all mAbs administered by IV infusion, infusion-related reactions to SYNT001 are possible. In general, infusion reactions to mAbs observed in human studies typically develop

[figure not shown]
within 30 minutes to 2 hours after the initiation of drug infusion, although symptoms may be delayed for up to 24 hours. These infusion reactions can occur with the first dose of a mAb and are generally mild in severity, although severe and even fatal reactions can occur.

Allergic and/or infusion-related reactions include hypersensitivity reactions and cytokine release syndromes. These reactions are experienced by subjects during or within hours of the infusion of mAb therapy. Symptoms can include flushing, alterations in heart rate and blood pressure, dyspnea, bronchospasm, back pain, fever, urticaria, edema, nausea, and all types of rashes. Anaphylaxis is recognized as a severe, life-threatening, generalized, or systemic reaction. This is a medical emergency characterized by rapidly developing life-threatening airway and/or breathing and/or circulation problems usually associated with skin or mucosal changes.

[figure not shown]
Management of Grade 1 infusion reactions include interrupting the infusion or decreasing the rate of infusion by 50% and observing. Symptoms may also be treated as needed with medications such as diphenhydramine, hydrocortisone, or acetaminophen, either alone or in combination, depending on the subject's signs and symptoms. If the infusion is interrupted or the infusion rate is decreased, it is important to note that all study drug infusions must be completed within 4 hours of SYNT001 preparation.

Management of Grade 2 and higher infusion reactions should include stopping the infusion of study drug. Continued treatment with SYNT001 is prohibited following Grade 2 or higher infusion reactions. See [Figure 2](#) and [Figure 3](#) for details on the management of Grade 2 and Grade 3 infusion reactions. Allergic or IRRs will be graded in severity and managed based on NCI CTCAE Version 4.03 (see [Table 8](#)).

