**Figure 2. Management of Moderate (Grade 2) Infusion Reactions**

**Figure 3. Management of Severe (Grade 3 or Higher) Infusion Reactions**

**Table 8. Grading and Management of Allergic or Infusion-Related Reactions**

Adverse Event	Grade				
	1	2	3	4	5
Infusion-related reaction	Mild transient reaction; infusion interruption not indicated; intervention not indicated	Therapy or infusion interruption indicated but responds promptly to symptomatic treatment (eg, antihistamines, non-steroidal anti-inflammatory drugs [NSAIDS], narcotics, IV fluids); prophylactic medications indicated for ≤24 hours	Prolonged (eg, not rapidly responsive to symptomatic medication and/or brief interruption of infusion); recurrence of symptoms following initial improvement, hospitalization indicated for clinical sequelae	Life-threatening consequences; urgent intervention required	Death
Allergic reaction	Transient flushing or rash, drug fever <38.0°C. Intervention not indicated	Therapy or infusion interruption indicated but responds promptly to symptomatic treatment (eg, antihistamines, NSAIDS, narcotics, IV fluids); prophylactic medications indicated for ≤24 hours	Prolonged (eg, not rapidly responsive to symptomatic medication and/or brief interruption of infusion); recurrence of symptoms following initial improvement, hospitalization indicated for clinical sequelae (eg, renal impairment, pulmonary infiltrates)	Life-threatening consequences; urgent intervention required	Death
Anaphylaxis	–	–	Symptomatic bronchospasm, with or without urticarial; parenteral intervention indicated; allergy-related edema/angioedema; hypotension	Life-threatening consequences; urgent intervention required	Death
Cytokine release syndrome	Mild reaction; infusion interruption not indicated; intervention not indicated	Therapy or infusion interruption indicated but responds promptly to symptomatic treatment (eg, antihistamines, NSAIDS, narcotics, IV fluids); prophylactic medications indicated for ≤24 hours	Prolonged (eg, not rapidly responsive to symptomatic medication and/or brief interruption of infusion); recurrence of symptoms following initial improvement, hospitalization indicated for clinical sequelae (eg, renal impairment, pulmonary infiltrates)	Life-threatening consequences; pressor or ventilator support indicated	Death

Abstracted from NCI CTCAE Version 4.03.

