Infusion related reaction	Mild transient reaction; infusion interruption not indicated; intervention not indicated	Therapy or infusion interruption indicated but responds promptly to symptomatic treatment (e.g., antihistamines, NSAIDS, narcotics, IV fluids); prophylactic medications indicated for <=24 hrs	Prolonged (e.g., not rapidly responsive to symptomatic medication and/or brief interruption of infusion); recurrence of symptoms following initial improvement; hospitalization indicated for clinical sequelae	Life-threatening consequences; urgent intervention indicated	Death
Definition: A disorder characterized by adverse reaction to the infusion of pharmacological or biological substances.					
Infusion site extravasation	-	Erythema with associated symptoms (e.g., edema, pain, induration, phlebitis)	Ulceration or necrosis; severe tissue damage; operative intervention indicated	Life-threatening consequences; urgent intervention indicated	Death
Definition: A disorder characterized by leakage of a pharmacologic or a biologic substance from the infusion site into the surrounding tissue. Signs and symptoms include induration, erythema, swelling, burning sensation and marked discomfort at the infusion site.					
Injection site reaction	Tenderness with or without associated symptoms (e.g., warmth, erythema, itching)	Pain; lipodystrophy; edema; phlebitis	Ulceration or necrosis; severe tissue damage; operative intervention indicated	Life-threatening consequences; urgent intervention indicated	Death
Definition: A disorder characterized by an intense adverse reaction (usually immunologic) developing at the site of an injection.					
Irritability	Mild; easily consolable	Moderate; limiting instrumental ADL; increased attention indicated	Severe abnormal or excessive response; limiting self care ADL; inconsolable	-	-
Definition: A disorder characterized by an abnormal responsiveness to stimuli or physiological arousal; may be in response to pain, fright, a drug, an emotional situation or a medical condition.					
Localized edema	Localized to dependent areas, no disability or functional impairment	Moderate localized edema and intervention indicated; limiting instrumental ADL	Severe localized edema and intervention indicated; limiting self care ADL	-	-
Definition: A disorder characterized by swelling due to excessive fluid accumulation at a specific anatomic site.					

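### Section 10.3.2 manages Grade 1 infusion reactions with interruption and drugs, yet under the Table 8 grading it invokes a reaction with either one indicated is Grade 2, where continued SYNT001 is banned

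*Protocol*

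**What the plan says.** Protocol section 10.3.2 gives a management rule by grade and names the grading scale.

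- Grade 1: "Management of Grade 1 infusion reactions include interrupting the infusion or decreasing the rate of infusion by 50% and observing". It adds: "Symptoms may also be treated as needed with medications such as diphenhydramine, hydrocortisone, or acetaminophen". It then notes: "If the infusion is interrupted or the infusion rate is decreased, it is important to note that all study drug infusions must be completed". The limit is 4 hours from preparation, so a Grade 1 infusion that was paused is expected to be finished.
- Grade 2 and above: the infusion is stopped, and "Continued treatment with SYNT001 is prohibited following Grade 2 or higher infusion reactions".
- Scale: "Allergic or IRRs will be graded in severity and managed based on NCI CTCAE Version 4.03", with a pointer to Table 8.

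Table 8 describes a Grade 1 infusion-related reaction as "Mild transient reaction; infusion interruption not indicated; intervention not indicated" and a Grade 2 reaction as "Therapy or infusion interruption indicated but responds promptly to symptomatic treatment". Appendix 1 has the same Grade 2 entry: "Therapy or infusion interruption indicated but responds promptly to symptomatic treatment (e.g., antihistamines, NSAIDS, narcotics, IV fluids".

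Section 7.12 (Corticosteroids) makes an exception to its stable-dose rule for subjects whose infusion reaction needs corticosteroids in its management. The investigator may then give them steroids preventively before later SYNT001 infusions. Item 4 of the prohibited medications in 7.12 has a related exception for IV steroids before an infusion, for subjects who were given corticosteroids to treat an earlier reaction. The synopsis carries both provisions. None of them sets a grade limit.

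**The concern.** The Grade 1 paragraph prescribes actions which, once indicated, move the event to Grade 2 on the scale that the same section names as governing. Grade 2 is also where SYNT001 is withdrawn. The wording mismatch therefore falls on the boundary that decides whether a subject is exposed again.

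Two things are at stake. The first is subject safety: section 2.2 reports one monkey death attributed to an immune-evoked infusion reaction that correlated with anti-drug antibodies, and section 7.5.6 foresees allergic reactions from such antibodies. A re-exposure rule should not depend on which sentence a site reads. The second is the safety data: adverse events are summarised by severity under a primary endpoint (sections 3 and 11.4.3.1), so sites that grade the same reaction differently blur that summary.

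**Working it through.** No calculation in the plan applies here. The check is a comparison of the texts.

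**Step 1. What Table 8 and Appendix 1 say.** Table 8 has four reaction types. Anaphylaxis has no Grade 1 entry. Of the other three (infusion-related reaction, allergic reaction, cytokine release syndrome), 3 of 3 Grade 1 entries say intervention is not indicated, and 2 of 3 also say interruption is not indicated (the allergic reaction entry does not mention interruption). All three Grade 2 entries begin at therapy or interruption being indicated. Appendix 1 agrees in substance for all three, so Table 8 is not a copying slip.

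**Step 2. One reaction, two routes.** Take a reaction with mild symptoms for which the investigator judges a pause and hydrocortisone to be indicated, and which settles promptly.

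- By the Grade 1 paragraph of 10.3.2: Grade 1, infusion resumed and completed within the time limit, later infusions given.
- By Table 8, which 10.3.2 names as the basis for grading and management: Grade 2, infusion stopped, continued SYNT001 prohibited.

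Both routes follow the written text.

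**Step 3. The steroid exception under each route.**

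| Provision | Grade 1 paragraph taken alone | Table 8 grading governs |
|---|---|---|
| 7.12 Corticosteroids and its synopsis counterpart (reaction needed corticosteroids) | No conflict: hydrocortisone is listed for Grade 1 and dosing continues | Conflict: the reaction is at least Grade 2, so no later infusion is allowed |
| 7.12 prohibited item 4 and its synopsis counterpart (subject was given corticosteroids) | No conflict | Conflict only if the steroid was indicated |

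The second conflict therefore follows from the first and is conditional on it.

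**Step 4. Whether other text settles it.** The individual stopping rule in 9.5.3 works by investigator or sponsor judgement and fixes neither the grade nor re-dosing after an infusion reaction. Figures 2 and 3 are titled for Grade 2 and for Grade 3 or higher. Their content is not in the text available here, so what they say about rechallenge is unknown.

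**The case against.** The best reply is that *indicated* is not the same as *done*. Table 8 grades by what is indicated, while 10.3.2 lets symptoms be treated as needed, so an investigator could pause or medicate a mild reaction as a precaution and still call it Grade 1. This has some force: a pause does not by itself prove Grade 2, and slowing the infusion is not mentioned in Table 8 at all. It does not rescue the text. Section 10.3.2 sets out these actions as the management of Grade 1, not as optional precautions, and the corticosteroid paragraph in 7.12 and its synopsis counterpart speak of a reaction for which steroids are necessary.

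A reader might infer that 7.12 and the synopsis contradict the ban outright. The documents do not support that. On the Grade 1 paragraph alone, a subject can receive hydrocortisone, stay at Grade 1 and be dosed again, and the exception has a clear use. The prohibited-medication item is weaker still, since being given a steroid does not establish that it was indicated.

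Two further points stand. Figures 2 and 3 might add a rule on Grade 2 rechallenge, so deleting the exception before checking them would go too far. And where the ban should begin is a clinical choice. The documents show that two rules are in force, not which one the sponsor meant.

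**Conclusion.** The inconsistency is real and should be fixed. Section 10.3.2 gives two outcomes for a reaction in which interruption or drug therapy is indicated: re-dosing, or a permanent stop. The conflict with the steroid exception holds if Table 8 grading governs, and not otherwise.

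Its frequency cannot be stated, because the protocol gives no infusion-reaction rate. Section 2.2 says that among seven Cohort 1 subjects at 10 mg/kg, headache was the only drug-related event reported in more than one subject. An infusion reaction reported as a drug-related event under its own term thus occurred in at most 1 of 7. That says little about the 30 mg/kg loading doses.

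A reader might also want to count the infusions still to come: after the first dose in Cohort 2, 3 + 5 - 1 = 7 on the base schedule, or 84/7 + 1 - 1 = 12 on the weekly option. Those counts describe the dosing schedule. They do not measure the size of the error.

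The conclusion assumes that the ban covers later infusions, which is its plain wording, and that Figures 2 and 3 do not override the text.

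**What to change.** In 10.3.2, state that a reaction for which interruption or drug therapy is indicated is Grade 2 by Table 8, and limit the Grade 1 text to observation with optional rate reduction. In 7.12 and the synopsis, add that the steroid exception applies only to subjects still eligible for SYNT001 under 10.3.2.

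If the sponsor intends rechallenge after a promptly resolving Grade 2 reaction, start the ban at Grade 3 instead and say that the steroid exception covers those subjects. In either case, check that Figures 2 and 3 match the text.

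The cost is wording in three places, a check of two figures and a notice to sites, with no new data collection. The downside of keeping the ban at Grade 2 is that some subjects with brief reactions would stop SYNT001.
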